4.2.2 EXCLUSION CRITERIA

1. Have received the following prior or current anticancer therapy:
 - a. Radiotherapy within the last 6 weeks (except for symptom control and where the lesions will not be used as measurable disease)
 - b. Endocrine therapy during the previous 4 weeks except for luteinizing hormone releasing hormone (LHRH) agonists for prostate cancer

- c. Chemotherapy during the previous 4 weeks
- d. Immunotherapy during the previous 6 weeks
- e. Nitrosoureas or Mitomycin C during the previous 6 weeks
- f. Other IMPs during the 4 weeks before treatment
- g. Any prior treatment with a Chk1 inhibitor, or prior treatment with an ATR inhibitor within 6 months prior to receiving SRA737.

2. Other malignancy within the past 2 years with the exception of adequately treated tumors that are associated with an expected 5-year disease-free survival of approximately 95% or better.

3. Ongoing toxic manifestations of previous treatments greater than NCI-CTCAE Grade 1. Exceptions to this are alopecia or certain toxicities, which in the opinion of the investigator and the sponsor or sponsor's designee should not exclude the subject.

4a. For subjects in the Dose Escalation Phase that are not to be included in an Expansion Cohort: new or progressing brain metastases. Subjects with brain metastases that have been radiologically stable over an 8-week period may be included in this phase.

4b. For subjects in the Cohort Expansion Phase: present or prior brain metastases.

5. Women of childbearing potential (WOCBP) or women who are already pregnant or lactating. However, those patients who have a negative serum or urine pregnancy test before enrollment and agree to use two forms of contraception as per Appendix 4 or agree to sexual abstinence, effective from the first administration of SRA737, throughout the trial and for six months afterwards are considered eligible.

6. Male subjects with partners of childbearing potential (unless they agree to take measures not to father children by using a barrier method of contraception as per Appendix 4 from the first administration of SRA737 through the trial and for 6 months after their final SRA737 dose). Men with pregnant or lactating partners must be advised to use barrier method contraception (eg, condom plus spermicidal gel) to prevent exposure of the fetus or neonate.

7. Major surgery from which the subject has not yet recovered.

8. At high medical risk because of non-malignant systemic disease including active uncontrolled infection.

9. Known to be serologically positive for hepatitis B, hepatitis C or human immunodeficiency virus (HIV).

10. Serious cardiac condition, such as concurrent congestive heart failure, prior history of class III/ IV cardiac disease (New York Heart Association [NYHA] refer to Appendix 3), left ventricular ejection fraction < 45% at baseline, history of cardiac

ischemia within the past 6 months, or prior history of cardiac arrhythmia requiring treatment.

11. Prior bone marrow transplant or extensive radiotherapy to greater than 25% of bone marrow within 8 weeks.
12. Peanut allergy. Refer to Section 6 for additional details.
13. QTcF > 450 msec in adult males and > 470 msec in adult females.
14. Impairment of gastrointestinal (GI) function or GI disease that may significantly alter the absorption of SRA737 (eg, ulcerative diseases, uncontrolled nausea, vomiting, diarrhea, or malabsorption syndrome).
15. Not able to swallow capsules without chewing or crushing.
16. Is a participant or plans to participate in another interventional clinical trial, whilst taking part in this Phase 1/2 study of SRA737. Participation in an observational trial or interventional clinical trial which does not involve administration of an IMP and which would not place an unacceptable burden on the subject in the opinion of the investigator and Sponsor or Sponsor's designee would be acceptable.
17. Any other condition which in the investigator's opinion would not make the subject a good candidate for the clinical trial.

5 DOSAGE AND TREATMENT ADMINISTRATION

5.1 STARTING DOSE AND REGIMEN

SRA737 will be administered orally on a continuous daily schedule. The starting dose for Cohort 1 is 20 mg per day. Each cycle of continuous treatment will last 28 days, and subjects may continue as long as none of the treatment discontinuation criteria (see Section 5.6) are met.

5.2 ALTERNATIVE DOSING REGIMEN

Consideration may be given to alternative dosing schedules at any time during the study, following discussion between the Sponsor and investigators. It may be more likely that an alternative schedule will be needed if the C_{min} at the MTD of SRA737 is less than 100 nM (the concentration below which sustained Chk1 inhibition is not anticipated), and/or if safety and tolerability data, PK and/or PDn data (eg, time to onset and time to recovery of myelosuppression) indicate that an alternative dosing schedule would be more suitable. Alternative schedules may include, but are not limited to, the following examples: 5 days of dosing followed by 2 days of non-dosing each week; 1 week of daily dosing followed by 1, 2, or 3 weeks of non-dosing; 2 or 3 weeks of daily dosing followed by 1, or 2 weeks of non-

dosing; or twice daily dosing. Alternative dosing schedule cohorts may be recruited in parallel to or instead of the continuous schedule cohorts.

The initial starting dose for an alternate schedule will depend on the safety, tolerability and PK results from the previous schedule cohorts. If an alternative schedule is to be tested after an MTD has been identified with the previous schedule, the starting total weekly dose for the new schedule will not exceed the total weekly dose at the MTD for the previous schedules. If an MTD has not been identified with the previous schedule, a dose escalation step may occur; however, the dose escalation may not exceed 50% based on the total weekly dose.

5.3 DURATION OF TREATMENT

Treatment should continue until disease progression unless the subject meets one of the other treatment discontinuation criteria outlined in Section 5.6.

5.4 DOSE MODIFICATIONS

The schedule and/or dose may be reduced for all subjects depending on emerging safety information. Decisions regarding treatment modification for individual subjects will be based on the following assessments:

- Laboratory values and AE observations from the day of dosing, to determine if treatment can be administered or should be withheld;
- Lowest (nadir) laboratory values and worst grade AE observations since the previous dose of study drug(s), to determine if a dose reduction is recommended.

Decisions to delay or adjust the dose of SRA737 should be made conservatively, using the guidelines for the most severe AEs and the worst scenario of the recommended dose reduction(s). Once the dose has been reduced, it should not be re-escalated. If any subject requires a delay in dosing for more than 28 days, the subject should be discontinued from treatment (see Section 5.6).

5.4.1 DOSE REDUCTIONS OR DELAYS

Guidelines for dose delays due to AEs are provided in Table 2.

Table 2. Dose Delay and Discontinuation Guidelines

Event	Recommended Action
Grade 3 neutropenia or Grade 3 thrombocytopenia	
Recommend twice weekly monitoring of blood tests if the subject is to continue dosing.
Grade 4 neutropenia or thrombocytopenia or Any non-hematologic \geq Grade 3 SRA737-related toxicity*	
Consider dose interruptionIf toxicities have not resolved to \leq Grade 1 or \leq 1 grade worse than baseline with a dose interruption, continue to delay treatment for up to 4 weeks. If no recovery after 4-week delay, discontinue treatment.
If toxicities have resolved to \leq Grade 1 or \leq 1 grade worse than baseline, treatment may be reinitiated. Consider resumption of treatment at the next lowest dose level for the schedule under investigation or at a reduced dose at an alternative, intermittent schedule.

*Exceptions may include nausea, vomiting or diarrhea lasting < 48 hours, asymptomatic biochemical abnormalities lasting < 5 days, Grade 3 fatigue (unless there was an increase in severity of > 2 grades from baseline), or other event agreed with the Sponsor or Sponsor's designee.

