3.4 DEFINITION OF DOSE LIMITING TOXICITY

The DLT window is defined from the first Day -7 to Day -4 dose until the end of Cycle 1 (up to 35 days).

A DLT is defined as any highly probably or probably SRA737-related event of:

- Grade 4 neutropenia or thrombocytopenia that lasts for > 7 days despite withholding dosing and/or providing supportive care (eg, hematopoietic growth factors)

Note: In the event of a Grade 4 neutropenia or Grade 4 thrombocytopenia, a full blood count must be performed at least on Day 7 after the onset of the event to determine if a DLT has occurred. The investigator must continue to monitor the subject closely until resolution to ≤ Grade 3.

- Febrile Neutropenia
- A ≥ Grade 3 thrombocytopenia with ≥ Grade 3 bleeding
- A ≥ Grade 3 nonhematological toxicity with the following possible exceptions per Cohort Review discussion:
 - Alopecia of any grade
 - Grade 3 or 4 nausea or vomiting in subjects that have not received optimal treatment with anti-emetics
 - Grade 3 or 4 diarrhea in subjects that have not received optimal treatment with anti-diarrheal medication
 - Transient, asymptomatic Grade 3 biochemical abnormalities if agreed by the Medical Monitor and the Chief Investigator
 - Grade 3 fatigue, unless there is an increase by at least 2 grades from baseline (classed as the grade prior to first dose)
- Inability to receive 75% of planned dose in the first cycle during the DLT window due to drug-related toxicity

DLTs defined above will be considered for the purposes of dose escalation decisions; however, should cumulative toxicity become apparent this will also be taken into consideration when determining either the next dose level or the RP2D(s).

All DLTs must be reported to the sponsor or sponsor's delegate within 24 hours of site staff becoming aware of the DLT, including any change made to the grade or causality of an AE that may alter its DLT status, as this may affect dose escalation decision making.

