10.1.4 DETERMINING ADVERSE EVENT CAUSALITY

The relationship of an AE to the IMP is determined as follows.

Highly probable	
Starts within a time related to the IMP administration andNo obvious alternative medical explanation
Probable	
Starts within a time related to the IMP administration andCannot be reasonably explained by known characteristics of the subject's clinical state
Possible	
Starts within a time related to the IMP administration andA causal relationship between the IMP and the AE is at least a reasonable possibility
Unlikely	
The time association or the subject's clinical state is such that the trial drug is not likely to have had an association with the observed effect
Not related	
The AE is definitely not associated with the IMP administered

Note: Drug-related refers to events assessed as possible, probable or highly probable.

The investigator must endeavor to obtain sufficient information to determine the causality of the AE (ie, IMP, other illness, progressive malignancy etc.) and must provide his/her opinion of the causal relationship between each AE and IMP. This may require instituting supplementary investigations of significant AEs based on their clinical judgement of the likely causative factors and/or include seeking a further opinion from a specialist in the field of the AE.

The following guidance should be taken in to account when assessing the causality of an AE:

- Previous experience with the IMP and whether the AE is known to have occurred with the IMP
- Alternative explanations for the AE such as concomitant medications, concurrent illness, non-medicinal therapies, diagnostic tests, procedures or other confounding effects
- Timing of the events between administration of the IMP and the AE
- IMP PK and evidence, if any, of overdose
- De-challenge, that is, if the IMP was discontinued or the dosage reduced, what happened to the adverse reaction?
- Re-challenge, that is, what happened if the IMP was restarted after the AE had resolved?

10.1.5 *EXPECTEDNESS*

Assessment of expectedness for SRA737 will be made by the Sponsor or Sponsor designee's Pharmacovigilance Department against the current version of the investigator's Brochure.

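### Table 2's dosing footnote is looser than the DLT definition in two places: Grade 3 fatigue that has risen exactly 2 grades, and short asymptomatic Grade 4 biochemical values

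*Protocol*

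**What the plan says.** Two parts of the Protocol deal with severe non-hematologic toxicity.

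**Section 3.4 (DLT definition).** It opens with a causality limit: "A DLT is defined as any highly probably or probably SRA737-related event of". Non-hematologic toxicity of Grade 3 or worse counts, subject to a list introduced as "nonhematological toxicity with the following possible exceptions per Cohort Review discussion". Two items on that list matter here:

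- Fatigue: "Grade 3 fatigue, unless there is an increase by at least 2 grades from baseline". Baseline is the grade before the first dose.
- Biochemistry: "Transient, asymptomatic Grade 3 biochemical abnormalities if agreed by the Medical Monitor and the Chief Investigator".

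**Section 5.4.1, Table 2 (dosing guidance).** For related non-hematologic toxicity of Grade 3 or worse, the site is advised to consider an interruption. A footnote to that row begins: "Exceptions may include nausea, vomiting or diarrhea lasting < 48 hours, asymptomatic biochemical abnormalities lasting < 5 days". It continues with "Grade 3 fatigue (unless there was an increase in severity of > 2 grades from baseline" and ends with an open category, "or other event agreed with the Sponsor" or its designee.

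The row is not restricted to probable causality. Section 10.1.4 says: "Drug-related refers to events assessed as possible, probable or highly probable". Nothing in the Protocol or SAP explains why the fatigue thresholds differ or why only one of the two biochemical exceptions carries a grade.

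**The concern.** The two fatigue clauses have nearly the same form but a different boundary. One closes at a rise of 2 grades; the other closes only above 2. The two biochemical clauses also pair up, but the footnote omits the grade, although the row it qualifies includes Grade 4.

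A site investigator deciding whether to hold the drug will turn to Table 2, the event-specific dosing guidance. That reader can find a named exception for an event that Section 3.4 can count as dose-limiting. In a first-in-human trial with continuous daily dosing, an event serious enough to count against a dose level should not, without explanation, be listed among the exceptions to the advice to consider a hold. What is at stake is the clarity of individual dosing decisions.

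**Working it through.** The Protocol gives no figure to reproduce and no event frequencies. The check sets the two rules side by side and applies each to every relevant grade.

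**Fatigue.** Inputs: the event is Grade 3, so the rise is 3 minus the baseline grade. Section 3.4 closes its exception when the rise is ≥ 2; Table 2 closes its exception when the rise is > 2.

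| Baseline grade | Rise | Section 3.4 exception | Table 2 exception | Same? |
|---|---|---|---|---|
| 0 | 3 − 0 = 3 | closed (3 ≥ 2) | closed (3 > 2) | yes |
| 1 | 3 − 1 = 2 | closed (2 ≥ 2) | open (2 is not > 2) | **no** |
| 2 | 3 − 2 = 1 | open (1 < 2) | open (1 is not > 2) | yes |

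The rules disagree for 1 of 3 baseline grades. That baseline is admissible: exclusion criterion 3 (Section 4.2.2) bars residual toxicity of earlier treatment only above Grade 1.

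The overlap needs two further conditions from Section 3.4. The event must be judged probably or highly probably related, and it must fall between the first dose (Day −7 to Day −4) and the end of Cycle 1. A possibly related event is drug-related for Table 2 but is not a DLT, so no conflict arises there.

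**Biochemistry.** Take a related, asymptomatic abnormality lasting under 5 days, with the same causality and window conditions.

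| Grade | Section 3.4 exception | Table 2 exception |
|---|---|---|
| 3 | available, if the two named roles agree | available |
| 4 | not available | available, because no grade is stated |

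The difference of substance is Grade 4. The agreement step at Grade 3 is also absent from Table 2, but a rule for counting DLTs and a rule for dosing may reasonably differ on that, and it is not counted here.

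**After the change.** With the footnote closing at a rise of ≥ 2, the baseline 1 row reads closed (2 ≥ 2) in both columns. With the biochemical item limited to Grade 3, the Grade 4 row is unavailable in both. This holds for the named exceptions only; the sponsor-agreement clause would remain open to either event.

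**The case against.** The strongest reply is that the two lists do different jobs. Section 3.4 decides what counts in dose escalation, within a window of up to 35 days. Table 2 guides the care of one subject in any cycle. Nothing says their exceptions must match, and both lists are discretionary: the table advises, its exceptions are optional, and those in Section 3.4 are only possible ones.

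Other text also limits the risk. Section 5.4 asks for conservative decisions based on laboratory values and adverse events on the day of dosing. DLTs go to the sponsor within 24 hours. Section 3.7 bars intra-subject escalation after related toxicity of Grade 2 or worse at the current dose in the latest cycle. Section 5.6 allows discontinuation for unacceptable toxicity.

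Nor is Table 2 looser throughout. It covers possibly related events, and it sets a 5-day limit where Section 3.4 says only that the abnormality is transient. A duration under 5 days is known only once the value has resolved, so the footnote does not clearly license dosing through an unresolved Grade 4 value.

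Most of this stands, and it keeps the point minor. It does not remove the mismatch. The general instruction to be conservative supplies no threshold. A difference in purpose would justify a deliberate difference in cut-off, but the Protocol gives no reason for this one.

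A reader might also infer that Table 2 contradicts itself, because fatigue 2 grades above baseline would fail its restart test (Grade 1 or better, or no more than 1 grade above baseline). That does not follow: the restart test applies after an interruption, and an excepted event need not have led to one.

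**Conclusion.** The point holds as a minor patient-safety alignment of advisory guidance. For one of three baseline grades, related Grade 3 fatigue can be both a DLT and a named exception to the interruption advice. The same is true of a related asymptomatic Grade 4 biochemical value lasting under 5 days. Both statements assume that the event is probably or highly probably related and occurs in the DLT window. How often this would happen cannot be estimated from the documents.

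Two stronger readings are tempting, and the documents support neither:

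- *That the Protocol tells sites to keep dosing through a DLT.* It permits an exception to advice and directs nothing.
- *That the DLT count, the MTD or an analysis is affected.* DLT status rests on Section 3.4 alone, and Section 3.5 uses that definition to set the MTD. No statistical figure in the Protocol or SAP depends on the Table 2 footnote.

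The nausea, vomiting and diarrhea exceptions are not part of the finding.

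**What to change.** Make two edits to the footnote of Table 2:

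1. In the fatigue item, replace > 2 grades with ≥ 2 grades.
2. In the biochemical item, add that it applies to Grade 3 abnormalities only, keeping the 5-day limit.

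A 2-grade fatigue rise, or a short Grade 4 value, could then be excepted only through the clause the footnote already has, "or other event agreed with the Sponsor" or its designee. The exception would become an agreed decision instead of one the site can take from the list.

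If the looser cut-offs were intended, one sentence in Section 5.4.1 saying so, with the reason, would settle the discrepancy.

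The cost is protocol wording only, with no added subjects, assessments or analyses. The one drawback is slightly less site discretion without sponsor agreement.

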5.5 SUPPORTIVE CARE, CONCOMITANT MEDICATIONS, AND STUDY RESTRICTIONS

5.5.1 OPTIONAL AND ALLOWED CONCOMITANT MEDICATIONS

Concomitant medication may be given as medically indicated. Details (including name and start and stop dates of the concomitant medication given) must be recorded in the subject's medical records and details entered into the electronic case report form (eCRF).

5.5.1.1 Granulocyte-colony Stimulating Factor

Subjects should not be administered G-CSF prophylactically but may be administered as medically indicated.

5.5.1.2 Palliative Radiotherapy

Palliative radiotherapy may be given concomitantly for the control of bone pain or other symptoms. Irradiated lesions will not be evaluable for response.

5.5.1.3 Contraception Usage

To be eligible for this study, WOCBP (as defined per Appendix 4) and male subjects with partners of childbearing potential must use 2 forms of contraception or agree to sexual

abstinence effective from the first administration of SRA737 through the trial and for 6 months afterwards. See Appendix 4 for more information.

